5.1.1 Protocol Therapy

5.1.1.1 Lenalidomide Description

REVLIMID[®] (lenalidomide), a thalidomide analogue, is an immunomodulatory agent with anti-angiogenic properties. The chemical name is 3-(4-amino-1-oxo 1,3-dihydro -2*H*-isoindol-2-yl) piperidine-2,6-dione and it has the following chemical structure:

Chemical Structure of Lenalidomide

3-(4-amino-1-oxo 1,3-dihydro-2*H*-isoindol-2-yl) piperidine-2,6-dione

The empirical formula for lenalidomide is C₁₃H₁₃N₃O₃, and the gram molecular weight is 259.3.

Lenalidomide is off-white to pale-yellow solid powder. It is soluble in organic solvent/water mixtures, and buffered aqueous solvents. Lenalidomide is more soluble in organic solvents and low pH solutions. Solubility was significantly lower in less acidic buffers, ranging from about 0.4 to 0.5 mg/ml. Lenalidomide has an asymmetric carbon atom and can exist as the optically active forms S(-) and R(+), and is produced as a racemic mixture with a net optical rotation of zero.

5.1.1.2 CLINICAL PHARMACOLOGY

Mechanism of Action:

The mechanism of action of lenalidomide remains to be fully characterized. Lenalidomide possesses immunomodulatory and antiangiogenic properties. Lenalidomide inhibited the secretion of pro-inflammatory cytokines and increased the secretion of anti-inflammatory cytokines from peripheral blood mononuclear cells. Lenalidomide inhibited cell proliferation with varying effectiveness (IC₅₀s) in some but not all cell lines. Of cell lines tested, lenalidomide was effective in inhibiting growth of Namalwa cells (a human B cell lymphoma cell line with a deletion of one chromosome 5) but was much less effective in inhibiting growth of KG-1 cells (human myeloblastic cell line, also with a deletion of one chromosome 5) and other cell lines without chromosome 5 deletions. Lenalidomide inhibited the expression of cyclooxygenase-2 (COX-2) but not COX-1 in vitro.

5.1.1.3 Pharmacokinetics and Drug Metabolism:

Absorption:

Lenalidomide, in healthy volunteers, is rapidly absorbed following oral administration with maximum plasma concentrations occurring between 0.625 and 1.5 hours post-dose. Co-administration with food does not alter the extent of absorption (AUC) but does reduce the maximal plasma concentration (C_{max}) by 36%. The pharmacokinetic disposition of lenalidomide is linear. C_{max} and AUC increase proportionately with increases in dose. Multiple dosing at the recommended dose-regimen does not result in drug accumulation.

Pharmacokinetic analyses were performed on 15 multiple myeloma patients treated in the phase I studies. Absorption was found to be rapid on both Day 1 and Day 28 with time to maximum blood levels ranging from 0.7 to 2.0 hours at all dose levels (5mg, 10mg, 25mg, and 50mg). No plasma accumulation was observed with multiple daily dosing. Plasma lenalidomide declined in a monophasic manner with elimination half-life ranging from 2.8 to 6.1 hours on both Day 1 and 28 at all 4 doses. Peak and overall plasma concentrations were dose proportional over the dosing range of 5mg to 50mg (Wu A. 2004, 2056). Exposure (AUC) in multiple myeloma patients is 57% higher than in healthy male volunteers.

Pharmacokinetic Parameters:

Distribution:

In vitro (¹⁴C)-lenalidomide binding to plasma proteins is approximately 30%.

Metabolism and Excretion:

The metabolic profile of lenalidomide in humans has not been studied. In healthy volunteers, approximately two-thirds of lenalidomide is eliminated unchanged through urinary excretion. The process exceeds the glomerular filtration rate and therefore is partially or entirely active. Half-life of elimination is approximately 3 hours.

5.1.1.4 Supplier(s)

Celgene Corporation will supply Revlimid® (lenalidomide) to study participants at no charge through the Revlimid REMS® program.

5.1.1.5 Dosage Form

Lenalidomide will be supplied as capsules for oral administration.

5.1.1.6 Packaging

Lenalidomide will be shipped directly to patients. Bottles will contain a sufficient number of capsules for one cycle of dosing.

5.1.1.7 Storage

Lenalidomide should be stored at room temperature away from direct sunlight and protected from excessive heat and cold.

5.1.1.8 Prescribing Information

Lenalidomide (Revlimid®) will be provided to research subjects for the duration of their participation in this trial at no charge to them or their insurance providers. Lenalidomide will be provided in accordance with Celgene Corporation's Revlimid REMS® program. Per standard Revlimid REMS® program requirements, all physicians who prescribe lenalidomide for research subjects enrolled into this trial, and all research subjects enrolled into this trial, must be registered in and must comply with all requirements of the Revlimid REMS® program. Prescriptions must be filled within 14 days, unless the patient is a female of childbearing potential, in which case the prescription must be filled within 7 days. **Only enough lenalidomide for one cycle of therapy will be supplied to the patient each cycle.**

5.2 Screening and Eligibility

The Investigator is responsible for keeping a record of all subjects who sign an Informed Consent Form for entry into the study. All subjects will be screened for eligibility. Screening procedures are outlined in Section 2, Schedule of Study Assessments and unless otherwise specified, must take place within 28 days prior to initiation of therapy.

Approximately 60 subjects with relapsed/refractory lymphoma undergoing ASCT in our institution will be screened for enrollment over a 36 month period. We anticipate that at least 28 patients will be categorized as having PET positive disease prior ASCT and be enrolled on study. Twenty four patients will proceed with the maintenance phase involving daily dosing with lenalidomide.

5.2.1 Inclusion Criteria

Subjects must meet the following inclusion/exclusion criteria to be registered to this study.

Inclusion criteria:

1. Able to understand and voluntarily sign the informed consent form.
2. Aged ≥ 18 years at the time of signing the informed consent form.
3. Able to adhere to the study visit schedule and other protocol requirements.
4. Biopsy-proven diagnosis of lymphoma (including diffuse large B-cell, mantle cell, follicular, marginal zone, peripheral T cell, small lymphocytic lymphoma with large cell transformation, and Hodgkin lymphomas).
5. Completion of at least 2 cycles of salvage chemotherapy, with pre-ASCT PET/CT imaging showing PET positive residual lesion(s) ($SUV > 2.5$).
6. Disease free of other malignancies for ≥ 2 years with exception of basal cell and squamous cell carcinomas of the skin, or carcinoma *in situ* of the cervix or breast.
7. Completion of high-dose chemotherapy with ASCT.
8. Hematologic recovery at 28-100 days after ASCT (defined as $ANC \geq 1,000$ and platelet count $\geq 60,000$).
9. All study participants must be registered into the mandatory Revlimid REMS® program and be willing and able to comply with the requirements of the Revlimid REMS® program
10. ECOG performance status of ≤ 2 at study entry (see Appendix B).
11. Patients undergoing planned consolidative radiation therapy must be finished with the therapy by day 100 after ASCT.
12. Laboratory test results within these ranges:
 - Absolute neutrophil count (ANC) $> 1,000/uL$
 - Platelet count $> 60,000/uL$
 - Serum creatinine ≤ 2.0 mg/dL
 - Total bilirubin $\leq 1.5 \times ULN$. Patients with known Gilbert's disease (as confirmed by study doctor) may participate with elevated bilirubin (serum bilirubin $\leq 2.0 \times ULN$) as long as their AST and ALT are within normal range.
 - AST (SGOT) and ALT (SGPT) $\leq 3 \times ULN$.

13. Females of childbearing potential (FCBP)[†] must have a negative serum or urine pregnancy test with a sensitivity of at least 50 mIU/mL within 10 – 14 days and again within 24 hours prior to prescribing lenalidomide for Cycle 1 (prescriptions must be filled within 7 days) and must either commit to continued abstinence from heterosexual intercourse or begin TWO acceptable methods of birth control, one highly effective method and one additional effective method AT THE SAME TIME, at least 28 days before she starts taking lenalidomide. FCBP must also agree to ongoing pregnancy testing. Men must agree to use a latex condom during sexual contact with a FCBP even if they have had a successful vasectomy. See Appendix: Risks of Fetal Exposure, Pregnancy Testing Guidelines and Acceptable Birth Control Methods.
14. Able to take aspirin (81 or 325 mg) daily as prophylactic anticoagulation (warfarin or low molecular weight heparin may be used for patients intolerant of aspirin or at the discretion of the treating physician).

5.2.2 Exclusion criteria:

1. A PET/CT or CT scan post-ASCT which shows disease progression.
2. Any serious medical condition, laboratory abnormality, or psychiatric illness that would prevent the subject from signing the informed consent form.
3. Pregnant or breast feeding females (lactating females must agree not to breast feed while taking lenalidomide).
4. Any condition, including the presence of laboratory abnormalities, which places the subject at unacceptable risk if he/she were to participate in the study or confounds the ability to interpret data from the study.
5. Use of any other experimental drug or therapy within 28 days of initiating treatment with lenalidomide.
6. Known hypersensitivity to thalidomide.
7. The development of erythema nodosum, a blistering or desquamating rash, while taking thalidomide or similar drugs.
8. Any prior use of lenalidomide.
9. Concurrent use of other anti-cancer agents or therapies during study treatment.
10. Known seropositive for or active viral infection with human immunodeficiency virus (HIV) or hepatitis B virus (HBV). Patients who are seropositive because of hepatitis B virus vaccine are eligible.

[†] A female of childbearing potential is a sexually mature female who: 1) has not undergone a hysterectomy or bilateral oophorectomy; or 2) has not been naturally postmenopausal for at least 24 consecutive months (i.e., has had menses at any time in the preceding 24 consecutive months).

5.3 Visit Schedule and Assessments

5.3.1 Screening/Enrollment - to take place at the time of hematologic recovery, between Days 28-100 post ASCT and within 28 days of initiation of treatment with lenalidomide:

- Review and signing of the Informed Consent Form
- Complete medical history, including prior and current medications, treatments, and anti-cancer therapies.
- Physical Exam and evaluation of ECOG PS
- Vital signs, including blood pressure, heart rate, oral temperature and weight
- Imaging with PET/CT scan or CT scan
- Electrocardiogram
- Serum Chemistry panel including sodium, potassium, chloride, CO₂, calcium, serum creatinine, BUN, total bilirubin, alkaline phosphatase, AST, ALT and TSH
- For women of childbearing potential, a serum pregnancy test must be performed 10-14 days and then within 24 hours prior to initiating treatment with lenalidomide
- Registration into Revlimid REMS® program

5.3.3 Cycle 1 of lenalidomide therapy

Within 7 days of initiating lenalidomide therapy

- Physical Examination and evaluation of ECOG PS (does not need to be repeated if previously performed within 7 days of starting treatment with lenalidomide)
- Vital signs: blood pressure, heart rate, temperature and weight (does not need to be repeated if previously performed within 7 days of starting treatment with lenalidomide)
- CBC with differential and platelets (does not need to be repeated if previously performed within 7 days of starting treatment with lenalidomide)
- Serum Chemistry panel including sodium, potassium, chloride, CO₂, calcium, serum creatinine, BUN, total bilirubin, alkaline phosphatase, AST, ALT (does not need to be repeated if previously performed within 7 days of starting treatment with lenalidomide)
- For women of childbearing potential, a serum pregnancy test must be performed 10-14 days and then within 24 hours prior to initiating treatment with lenalidomide

Cycle 1, Day 15 (+/- 3 days)

- Physical Examination and evaluation of ECOG PS
- Vital signs: blood pressure, heart rate, temperature and weight
- CBC with differential and platelets
- Serum Chemistry panel including sodium, potassium, chloride, CO₂, calcium, serum creatinine, BUN, total bilirubin, alkaline phosphatase, AST, ALT
- Serum pregnancy test (for women with irregular menses)
- Review of interim adverse events and concomitant medications

Cycle 1, Day 22 (+/- 3 days)

- CBC with differential and platelets

5.3.4 Cycles 2-24, Day 1 (+/- 7 days)

- Physical Examination and evaluation of ECOG PS
- Vital signs: blood pressure, heart rate, temperature and weight
- CBC with differential and platelets
- Serum Chemistry panel including sodium, potassium, chloride, CO₂, calcium, serum creatinine, BUN, total bilirubin, alkaline phosphatase, AST, ALT
- Serum pregnancy test (for women of child-bearing potential)
- Review of interim adverse events and concomitant medications

5.3.5 Radiographic Evaluations

Subjects will undergo radiographic evaluations to assess disease status at the timepoints listed below. Timing of radiographic evaluations may be altered based on clinical indication or the discretion of the treating physician.

- PET/CT after at least 2 cycles of salvage chemotherapy, but prior ASCT (using separate PET scan and dedicated CT scan performed within one week is acceptable)
- Imaging (PET/CT or CT scan) after ASCT, but prior Cycle 1 of lenalidomide therapy
- Imaging (PET/CT or CT scan) every 3 cycles during the first year of lenalidomide maintenance therapy (near end of Cycles 3, 6, 9, 12)
- Imaging (PET/CT or CT scan) every 4 cycles during second year of lenalidomide maintenance therapy (near end of Cycles 16, 20, 24)

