Patients will continue on lenalidomide maintenance for 24 months unless they develop progressive disease or unacceptable toxicity. The initial dose of maintenance therapy will be 10 mg of lenalidomide daily. We plan to adjust the dose according to specific dose modification criteria. To monitor response during lenalidomide maintenance, we will obtain post-ASCT imaging scan prior to starting lenalidomide and then every three months during the first year and every 4 months during the second year.

STUDY ENDPOINTSPrimary:

Dose limiting toxicity (DLT) as assessed by NCI CTCAE version 4.0

Secondary:

Progression free survival

Overall survival

STUDY DURATION: 60 months

DOSING REGIMEN: The initial dose of lenalidomide will be 10 mg daily. We will use a 3+3 design to determine tolerability of this dose in these heavily pretreated patients. We will allow decreasing lenalidomide to 5 mg daily according to specific dose modification criteria. We will stop the study if there are 2 subjects with DLTs at the 5 mg dose level.

TOTAL SAMPLE SIZE: We plan to enroll 24 evaluable patients with relapsed/refractory lymphoma who will initiate lenalidomide maintenance after ASCT during the initial 3 years of the study. It is likely that at least 28 patients may be enrolled to provide 24 evaluable patients.

DRUG SUPPLIES: Celgene Corporation will provide lenalidomide at no charge through the Revlimid REMS® program for study participants.

2 Schedule of Study Assessments

Procedure	Screening	Cycle 1			Cycles 2-24*	Discontinuation From Protocol Therapy	Follow-Up Phase
	On day 28-100 after ASCT at hematological recovery (<28 days before starting maintenance)	Day 1 [^]	Day 15	Day 22	Day 1		Every 3 months ⁸
Informed Consent	X						
Record lymphoma diagnosis, current medications	X						
Record prior anti-cancer therapies	X						
Physical examination, vital signs, weight	X	X ⁶	X		X	X	
ECOG performance status	X	X ⁶	X		X	X	
Imaging (PET/CT or CT scan)	X				X ⁴		
ECG	X						
CBC	X	X ⁶	X	X	X	X	
Serum chemistries ¹	X	X ⁶	X		X		
Pregnancy testing ^{2,3}	X	X ⁶			X	X	
Register patient into Revlimid REMS® program	X						
Baseline lesion assessment	X						
Prescribe lenalidomide via Revlimid REMS® ⁷	X				X		
Response assessment ⁴					X ⁴	X ⁴	
Record adverse events			X		X	X ⁵	
Record concomitant therapies/procedures		X			X	X	
Assess drug compliance/patient's study calendar					X	X	
Follow-up anti-cancer treatments							X
Follow-up progression and survival information							X

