5.1 Overall Design

Patients with relapsed/refractory lymphoma will undergo screening after ASCT following positive PET/CT scan. PET/CT scan results will be categorized as negative when no evidence of lymphoma is found by the radiologist at the time of the scan. PET/CT results will be categorized as positive when the intensity of any non-physiological signal is over 2.5 SUV, which is the measurement of FDG uptake often used to differentiate between benign and malignant lesions (Elstrom et al. 2003, 3875-3876; Al-Sugair and Coleman 1998, 303-319). Patients with diffuse bone marrow activity while on growth factors and with mild symmetric supraclavicular adipose tissue activity in the absence of focal lesions will be deemed as negative. All studies will be reviewed by a University of Pennsylvania nuclear medicine radiologist.

Patients with PET positive lesions who are candidates for ASCT as determined by their treating physician will undergo ASCT. The conditioning regimen will be at the discretion of the treating physician. Subsequent screening to determine eligibility will commence 28 to 100 days after ASCT at the time of count recovery defined as ANC \geq 1,000 and platelets \geq 60,000. Those patients who will undergo consolidative radiation after ASCT can proceed with maintenance treatment, but completion of their radiation and hematological recovery must occur by day 100 after ASCT.

To monitor response to lenalidomide, we will obtain post-ASCT imaging with PET/CT or CT scan prior to starting lenalidomide. During the lenalidomide maintenance, imaging (PET/CT or CT scan) will be performed at least every three months during the first year and at least every 4 months during the second year which reflects general frequency of imaging in this setting outside of this trial. Further imaging after 2 years of follow-up will be at discretion of the treating physician.

Patients will continue on lenalidomide for 24 cycles unless they develop progressive disease or unacceptable toxicity. One cycle is defined as 28 day period. We will initiate maintenance therapy with 10 mg of lenalidomide daily. We will dose adjust or hold lenalidomide for hematologic toxicity according to specific dose modification criteria.

[figure not shown]

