10.1 Design

This is a single arm phase I/II trial of lenalidomide maintenance for patients with high risk relapsed/refractory lymphomas who underwent high dose chemotherapy and ASCT. At 28-100 days post-ASCT, eligible patients will begin lenalidomide maintenance. The trial will be conducted in two stages. Phase I will evaluate the safety of lenalidomide implemented after ASCT by a 3+3 cohort design. Once the safety of a specific dose after ASCT is established, additional patients will be enrolled in phase II to evaluate the progression-free survival. PFS is a relevant endpoint for lenalidomide maintenance since it is expected to delay progression of disease post-ASCT. A monitoring rule for unacceptable toxicity due to lenalidomide will be followed during phase II.

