10.3 Endpoints

Dose-limiting toxicity (DLT) is defined as any grade 3 toxicity or higher that occurs during the first 28 days of therapy and is possibly, probably or definitely related to lenalidomide maintenance. Because certain levels of toxicity are considered acceptable in lymphoma therapy, the definition of DLT is limited to the following:

-Any grade 3 or higher non-hematologic toxicity possibly, probably or definitely related to lenalidomide.

-Grade 4 hematologic toxicity not attributable to progressive disease and that does not decrease to a grade 3 or less within 7 days of drug cessation.

-Lymphopenia of any grade and anemia of any grade are not considered a DLT.

-Nausea and vomiting are not considered DLTs unless they cannot be controlled with standard antiemetic therapy.

-Diarrhea is not considered a DLT unless it cannot be controlled with standard anti-diarrheal therapy.

-Nausea, vomiting, heartburn, anorexia, diarrhea, or constipation that improved to grade 1 or better within 2 days with the addition of symptom directed treatment will not be considered a DLT.

NCI Common toxicity criteria (CTC Version 4.0) grades will be employed. Toxicity unrelated to lenalidomide (i.e. clearly related to ASCT) will be scored separately.

Progression-free survival (PFS) is defined from date of ASCT (day 0) to first documented progression of disease, death due to any cause or last patient contact. Progression-free survival rate at 12 months (PFS12) is also of interest and is defined as the percentage of patients that are alive and progression-free at 12 months. Overall survival (OS) is defined as days from date of ASCT to death due to any cause or last patient contact.

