Patients are enrolled 28 to 100 days after ASCT (day 0). Patients who complete one full cycle of lenalidomide maintenance or who experience DLT during the first cycle will be considered evaluable for DLT determination. Patients who withdraw from the study prior to initiation of lenalidomide maintenance, or who initiate and discontinue lenalidomide maintenance before completing one full cycle and do not experience DLT, remain in the study population and are followed for PFS and OS but do not contribute to the determination of DLT. These patients will be included in the estimation of PFS and OS, according to an intent-to-treat analysis plan. A secondary analysis of PFS and OS will include only patients who complete at least one full cycle of lenalidomide or who experience DLT at any point during cycle 1 (“evaluable population”). Patients who did not progress will be censored at the time of last contact. Evaluable patients contribute to determination of DLT, PFS and OS. Evaluable patient outcomes will be compared to historical rates for PFS12.

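### PFS12 is timed from ASCT but scans are timed from the first lenalidomide dose, so for start days 30-100 the last scheduled scan before day 365 is 13-83 days old and a silent progression after it counts as a success

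*Combined protocol and SAP*

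**What the plan says.** Section 10.3 states that PFS "is defined from date of ASCT (day 0) to first documented progression of disease, death due to any cause or last patient contact". PFS12 is "defined as the percentage of patients that are alive and progression-free at 12 months". Both therefore run from the transplant, and a progression is dated when it is documented.

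The imaging calendar starts elsewhere. Section 10.1 says "At 28-100 days post-ASCT, eligible patients will begin lenalidomide maintenance". Section 5.3.5 then places first-year scans "every 3 cycles during the first year of lenalidomide maintenance therapy (near end of Cycles 3, 6, 9, 12", and Section 5.1 adds "One cycle is defined as 28 day period". Section 5.1 and Section 2 footnote 4 give the same plan in months of maintenance (every 3 in the first year, every 4 in the second).

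No section requires a scan at 12 months after ASCT, sets an assessment window for PFS12, or says how to class a progression first seen on a scan after that date. Section 10.6 asks for 12 months of observation, not for a disease assessment at month 12. Section 9.1 times the first report at 12 months from the start of lenalidomide, a third reference point.

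**The concern.** A patient who follows the schedule exactly can have imaging progression before day 365 that is first documented after it. Under Section 10.3 that patient is progression-free at 12 months. Late documentation can turn a failure into a success but not the reverse, and its extent depends on when each patient happened to start lenalidomide.

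PFS12 is secondary to DLT, but it carries the efficacy decision: Section 10.6 declares evidence of success if more than 4 of 24 evaluable patients are alive and progression-free, and Section 10.7 sizes the trial on that test. The rule has little room for upward drift in the observed rate.

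**Working it through.** **The plan's own figures.** The rule is at least 5 of 24 (Section 10.6), with a null rate of 10% and an alternative of 30% (Section 10.7). Exact binomial:
- P(X ≥ 5 | n = 24, p = 0.10) = 0.085, stated as 0.09
- P(X ≤ 4 | n = 24, p = 0.30) = 0.111, stated as 0.11
- power = 1 − 0.111 = 0.889, stated as 89%

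All three reproduce. The one-sided limit is 0.10.

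**Scan days.** Let s be the day of first dose after ASCT, 28 to 100 (Sections 10.1 and 10.3). With 28-day cycles, the scans at the end of cycles 3, 6, 9 and 12 fall on s + 84, s + 168, s + 252 and s + 336. Twelve months is taken as day 365.
- The cycle 12 scan falls on or before day 365 only if s ≤ 365 − 336 = 29.
- For s = 30 to 100 the last scan is cycle 9, at a gap of 365 − (s + 252) = 113 − s days: 83 down to 13.
- The next scan comes (s + 336) − 365 = s − 29 days after day 365: 1 up to 71.

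| First dose | Cycle 9 scan | Cycle 12 scan | Gap before day 365 | Next scan after day 365 |
|---|---|---|---|---|
| day 30 | 282 | 366 | 83 | 1 |
| day 60 | 312 | 396 | 53 | 31 |
| day 100 | 352 | 436 | 13 | 71 |

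The documents give no distribution of start days. If days 28-100 are equally likely (assumption), the gaps are 1 and 0 for days 28 and 29, plus 71 values averaging 48, so the mean is (1 + 0 + 71 × 48)/73 = 46.7 days.

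**Effect on the rule.** Assume a constant hazard from ASCT with true PFS12 of 10%: λ = −ln(0.10)/365 = 0.00631 per day. The proportion progression-free at the last scan, exp(−λ(365 − gap)), averages 0.1355 over the 73 start days. If a share f of gap progressions is silent until the next scan, the apparent rate is 0.10 + f × 0.0355.

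| f | Apparent PFS12 | P(X ≥ 5 of 24) |
|---|---|---|
| 0 | 10.0% | 0.085 |
| 0.25 | 10.9% | 0.113 |
| 0.5 | 11.8% | 0.144 |
| 1 | 13.6% | 0.22 |

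The tail probability reaches 0.10 at an apparent rate of about 10.5%, that is f = 0.005/0.0355, or about 14%.

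**Sensitivity.** The three biased figures (f = 0.25, 0.5, 1) become:
- 0.12, 0.16 and 0.25 if the hazard starts at first dose
- 0.107, 0.132 and 0.189 under the calendar-month version of the schedule

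**The case against.** **Scans near month 12.** A reader might infer that most patients have no scan near month 12. That depends on the window. With evenly spread start days, 75% have no scan within ±14 days of day 365, but 63% do have one within ±28 days, and no on-schedule patient is more than 42 days from a scan. This stands, so the claim is limited to the last scan before day 365. A scan soon after day 365 does not remove the problem, because Section 10.3 dates the event when it is documented.

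**Silent progressions.** A reader might also take 0.22 as the rule's real error rate. It is a ceiling. Section 2 footnote 4 lets progression be judged on the clinical picture as well as imaging, Section 7 provides monthly clinical assessment, and Section 5.3.5 lets scans move on clinical indication. Some gap progressions will be found in time. The documents give no basis for choosing the silent share, hence the range.

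**The benchmark.** The 10% null rests on historical rates that were themselves observed on some scan schedule. Section 5.1 says that the trial's imaging frequency reflects usual practice outside the trial. Much of the delay may therefore sit on both sides. This also stands: the historical scan schedule is not given, so the documents do not show that the comparison favours lenalidomide on balance. What remains is that the stated error rates refer to a true rate of 10%, which the present schedule does not measure without delay.

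**Convention.** Dating progression when documented is ordinary practice, and PFS is a secondary endpoint in a small single-arm trial. That limits the weight of the point, but PFS12 still determines the efficacy conclusion.

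**Conclusion.** The concern holds in this form. The endpoint and the scans run on different clocks, and for start days 30-100 the last scheduled scan before day 365 is 13 to 83 days old. Progression that is silent in that gap is counted as success. Relative to a true rate of 10%, type I error moves from 0.085 to about 0.11, 0.14 or, at most, 0.22 as the silent share goes from a quarter to a half to all; about 14% is enough to pass the 0.10 limit. These figures assume a constant hazard from ASCT, evenly spread start days and scans at cycle ends.

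The documents do not support saying that patients generally lack a scan around month 12, or that the result is biased by a known amount against the historical rate. The point should be addressed because the correction is cheap; it does not invalidate the design.

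**What to change.** **Schedule.** In Section 5.3.5, Section 5.1 and Section 2 footnote 4, anchor on-treatment scans to the ASCT date: for example months 3, 6, 9, 12, 16, 20 and 24 after ASCT, omitting any before the first dose, with the month-12 scan in a stated window such as day 365 ±14. This uses no more than the seven scans now planned and keeps the 3- and 4-month spacing, with the years counted from ASCT.

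Moving only the nearer of the cycle 9 and cycle 12 scans would not do. A day-80 start has scans on days 164, 248 and 332. Moving the last to day 365 leaves 201 days from day 164, more than two 3-month intervals (about 182 days) even if the middle scan is shifted too.

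**Analysis.** In Sections 10.3 and 10.6, determine PFS12 status from the month-12 scan. Add a sensitivity analysis that counts as a failure any progression first found on the first scan after a missed month-12 window, reported beside the Section 10.3 definition. It should stay a sensitivity analysis, because some of those patients will truly have progressed after day 365. Reconcile the 12-month clock in Section 9.1 at the same time.

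**Cost.** Scans no longer line up with cycle ends. The change to 4-month spacing comes at month 12 after ASCT, before a late starter's first year of maintenance is over, so the wording of Section 5.1 must change with it. The PFS12 estimate may be slightly less favourable.
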